#### 14.2.2.3.3 Determination of non-target lesion response

**Table 14-6 Response criteria for non-target lesions**

Response Criteria	Evaluation of non-target lesions
Complete Response (CR):	Disappearance of all non-target lesions. In addition, all lymph nodes assigned a non-target lesions must be non-pathological in size (< 10 mm short axis)
Progressive Disease (PD):	Unequivocal progression of existing non-target lesions. 
Non-CR/Non-PD:	Neither CR nor PD
Unknown (UNK)	Progression has not been documented and one or more non-target lesions have not been assessed or have been assessed using a different method than baseline  .

1. The assignment of PD solely based on change in non-target lesions in light of target lesion response of CR, PR or SD should be exceptional. In such circumstances, the opinion of the investigator or central reviewer does prevail.

2. It is recommended that the investigator and/or central reviewer should use expert judgment to assign a Non-UNK response wherever possible (see notes section for more details)

### Notes on non-target lesion response

- The investigator and/or central reviewer can use expert judgment to assign a non-UNK response wherever possible, even where lesions have not been fully assessed or a different method has been used. In many of these situations it may still be possible to identify equivocal progression (PD) or definitively rule this out (non-CR/Non-PD) based on the available information. In the specific case where a more sensitive method has been used indicating the absence of any non-target lesions, a CR response can also be assigned.
- The response for non-target lesions is **CR** only if all non-target non-nodal lesions which were evaluated at baseline are now all absent and with all non-target nodal lesions returned to normal size (i.e. < 10 mm). If any of the non-target lesions are still present, or there are any abnormal nodal lesions (i.e. ≥ 10 mm) the response can only be ‘**Non-CR/Non-PD**’ unless there is unequivocal progression of the non-target lesions (in which case response is **PD**) or it is not possible to determine whether there is unequivocal progression (in which case response is UNK).
- Unequivocal progression: To achieve “unequivocal progression” on the basis of non-target disease there must be an overall level of substantial worsening in non-target disease such that, even in presence of CR, PR or SD in target disease, the overall tumor burden has increased sufficiently to merit discontinuation of therapy. A modest “increase” in the size of one or more non-target lesions is usually not sufficient to qualify for unequivocal progression status. The designation of overall progression solely on the basis of change in non-target disease in the face of CR, PR or SD of target disease is therefore expected to be rare. In order for a PD to be assigned on the basis of non-target lesions, the increase in the extent of the disease must be substantial even in cases where there is no measurable disease at baseline. If there is unequivocal progression of non-target lesion(s), then at least one of the non-target lesions must be assigned a status of “Worsened”. Where possible, similar rules to those described in [Section 14.2.2.3.2](#) for assigning PD following a CR for the non-target lesion response in the presence of non-target lesions nodal lesions should be applied.

#### 14.2.2.3.4 New lesions

The appearance of a new lesion is always associated with Progressive Disease (PD) and has to be recorded as a new lesion in the New Lesion CRF page.

- If a new lesion is **equivocal**, for example because of its small size, continued therapy and follow-up evaluation will clarify if it represents truly new disease. If repeat scans confirm there is definitely a new lesion, then progression should be declared using the date of the first observation of the lesion
- If new disease is observed in a region which was **not scanned at baseline** or where the particular baseline scan is not available for some reason, then this should be considered as a PD. The one exception to this is when there are no baseline scans at all available for a subject in which case the response should be UNK, as for any of this subject's assessment (see [Section 14.2.2.3.5](#)).
- A **lymph node is considered as a “new lesion”** and, therefore, indicative of progressive disease if the short axis increases in size to ≥ 10 mm for the first time in the study plus 5 mm absolute increase.  
**FDG-PET:** can complement CT scans in assessing progression (particularly possible for ‘new’ disease).

### 14.2.2.3.5 Evaluation of overall lesion response

The evaluation of overall lesion response at each assessment is a composite of the target lesion response, non-target lesion response and presence of new lesions as shown below in [Table 14-7](#).

**Table 14-7 Overall lesion response at each assessment**

Target lesions	Non-target lesions	New Lesions	Overall lesion response
CR	CR	No	CR 
CR	Non-CR/Non-PD 	No	PR
CR, PR, SD	UNK	No	UNK
PR	Non-PD and not UNK	No	PR 
SD	Non-PD and not UNK	No	SD 
UNK	Non-PD or UNK	No	UNK 
PD	Any	Yes or No	PD
Any	PD	Yes or No	PD
Any	Any	Yes	PD

This overall lesion response also applies when there are no non-target lesions identified at baseline.

Once confirmed PR was achieved, all these assessments are considered PR.

As defined in [Section 14.2.2.3.3](#).

If there are no baseline scans available at all, then the overall lesion response at each assessment should be considered Unknown (UNK).

In some circumstances it may be difficult to distinguish residual disease from normal tissue. When the evaluation of complete response depends on this determination, it is recommended that the residual lesion be investigated (fine needle aspirate/biopsy) to confirm the CR.

## 14.2.3 Efficacy definitions

The following definitions primarily relate to subjects who have measurable disease at baseline. [Section 14.2.3.2.8](#) outlines the special considerations that need to be given to subjects with no measurable disease at baseline in order to apply the same concepts.

### 14.2.3.1 Best overall response

The best overall response is the best response recorded from the start of the treatment until disease progression/recurrence (taking as reference for PD the smallest measurements recorded since the treatment started). In general, the subject's best response assignment will depend on the achievement of both measurement and confirmation criteria.

The best overall response will usually be determined from response assessments undertaken while on treatment. However, if any assessments occur after treatment withdrawal the protocol should specifically describe if these will be included in the determination of best overall response and/or whether these additional assessments will be required for sensitivity or supportive analyses. As a default, any assessments taken more than 30 days after the last dose of study treatment will not be included in the best overall response derivation. If any alternative cancer therapy is taken while on study any subsequent assessments would ordinarily be excluded from the best overall response determination. If response assessments taken after withdrawal from study treatment and/or alternative therapy are to be included in the main endpoint determination, then this should be described and justified in the protocol.

Where a study requires confirmation of response (PR or CR), changes in tumor measurements must be confirmed by repeat assessments that should be performed not less than 4 weeks after the criteria for response are first met.

Longer intervals may also be appropriate. However, this must be clearly stated in the protocol. The main goal of confirmation of objective response is to avoid overestimating the response rate observed. In cases where confirmation of response is not feasible, it should be made clear when reporting the outcome of such studies that the responses are not confirmed.

- For non-randomized trials where response is the primary endpoint, confirmation is needed.
- For trials intended to support accelerated approval, confirmation is needed
- For all other trials, confirmation of response may be considered optional.

The best overall response for each subject is determined from the sequence of overall (lesion) responses according to the following rules:

- CR = at least two determinations of CR at least 4 weeks apart before progression where confirmation required or one determination of CR prior to progression where confirmation not required
- PR = at least two determinations of PR or better at least 4 weeks apart before progression (and not qualifying for a CR) where confirmation required or one determination of PR prior to progression where confirmation not required
- SD = at least one SD assessment (or better) > 11 weeks after randomization/start of treatment (and not qualifying for CR or PR).
- PD = progression ≤ 12 weeks after randomization/ start of treatment (and not qualifying for CR, PR or SD).
- UNK = all other cases (i.e. not qualifying for confirmed CR or PR and without SD after more than 11 weeks or early progression within the first 12 weeks)

The time durations specified in the SD/PD/UNK definitions above are based on the first 12-week tumor assessment frequency taking into account time windows for assessment. E.g. if the first assessment occurs at week 12 with a time window of +/- 7 days, a BOR of SD would require a SD or better response longer than 11 weeks after randomization/start of treatment.

Overall lesion responses of CR must stay the same until progression sets in, with the exception of a UNK status. A subject who had a CR cannot subsequently have a lower status other than a PD, e.g. PR or SD, as this would imply a progression based on one or more lesions reappearing, in which case the status would become a PD.

Once an overall lesion response of PR is observed (which may have to be a confirmed PR depending on the study) this assignment must stay the same or improve over time until progression sets in, with the exception of an UNK status. However, in studies where confirmation of response is required, if a subject has a single PR (≥30% reduction of tumor burden compared to baseline) at one assessment, followed by a <30% reduction from baseline at the next assessment (but not ≥20% increase from previous smallest sum), the objective status at that assessment should be SD. Once a confirmed PR was seen, the overall lesion response should be considered PR (or UNK) until progression is documented or the lesions totally disappear in which case a CR assignment is applicable. In studies where confirmation of response is not required after a single PR the overall lesion response should still be considered PR (or UNK) until progression is documented or the lesion totally disappears in which case a CR assignment is applicable.

Example: In a case where confirmation of response is required the sum of lesion diameters is 200 mm at baseline and then 140 mm - 150 mm - 140 mm - 160 mm - 160 mm at the subsequent visits. Assuming that non-target lesions did not progress, the overall lesion response would be PR - SD - PR - PR - PR. The second assessment with 140 mm confirms the PR for this subject. All subsequent assessments are considered PR even if tumor measurements decrease only by 20% compared to baseline (200 mm to 160 mm) at the following assessments.

If the subject progressed but continues study treatment, further assessments are not considered for the determination of best overall response.

Note: these cases may be described as a separate finding in the CSR but not included in the overall response or disease control rates.

The best overall response for a subject is always calculated, based on the sequence of overall lesion responses. However, the overall lesion response at a given assessment may be provided from different sources:

- Investigator overall lesion response
- Central Blinded Review overall lesion response
- Novartis calculated overall lesion response (based on measurements from either Investigator or Central Review)

The primary analysis of the best overall response will be based on the sequence of investigator overall lesion responses.

Based on the subjects' best overall response during the study, the following rates are then calculated:

**Overall response rate (ORR)** is the proportion of subjects with a best overall response of CR or PR. This is also referred to as 'Objective response rate' in some protocols or publications.

**Disease control rate (DCR)** is the proportion of subjects with a best overall response of CR or PR or SD. The objective of this endpoint is to summarize subjects with signs of "activity" defined as either shrinkage of tumor (regardless of duration) or slowing down of tumor growth.

**Clinical benefit rate (CBR)** is the proportion of subjects with a best overall response of CR or PR, or an overall lesion response of SD or Non-CR/Non-PD which lasts for a minimum time duration (with a default of at least 24 weeks in breast cancer studies). This endpoint measures signs of activity taking into account duration of disease stabilization.

Another approach is to summarize the progression rate at a certain time point after baseline. In this case, the following definition is used:

**Early progression rate (EPR)** is the proportion of subjects with progressive disease within 8 weeks of the start of treatment.

The protocol should define populations for which these will be calculated. The timepoint for EPR is study specific. EPR is used for the multinomial designs of (Dent 2001) and counts all subjects who at the specified assessment (in this example the assessment would be at 8 weeks  $\pm$  window) do not have an overall lesion response of SD, PR or CR. Subjects with an unknown (UNK) assessment at that time point and no PD before, will not be counted as early progressors in the analysis but may be included in the denominator of the EPR rate, depending on the analysis population used. Similarly when examining overall response and

disease control, subjects with a best overall response assessment of unknown (UNK) will not be regarded as “responders” but may be included in the denominator for ORR and DCR calculation depending on the analysis population (e.g. populations based on an ITT approach).

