### 10.4.1 Variable

Objective response rate (ORR) is defined as the proportion of subjects with best overall response (BOR) of either confirmed complete response (CR) or confirmed partial response (PR), as per local review and according to RECIST v1.1 (see Appendix 2 for details).

[REDACTED]

ORR will be calculated based on the FAS. ORR and its 95% confidence interval will be presented by treatment group.

As a supportive analysis, ORR as per blinded independent central review (BICR) will be presented by treatment group; along with 95% confidence intervals (see [Section 10.4.4](#)).

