### **10.4.3 Handling of missing values/censoring/discontinuations**

For the computation of ORR, all confirmed responses (CR or PR) reported up to the analysis cut-off will be included. Subjects with no valid radiological assessment or unconfirmed responses will be considered as non-responders. Subjects who were non-responders before initiation of subsequent anti-cancer therapy will still be non-responders. In particular, subjects with CR or PR at the last radiological assessment prior to cut-off and no response at the previous assessment are by definition unconfirmed and will be considered as non-responders for the primary analysis.

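### The protocol never sets aside Appendix 2's 30-day cut-off on best overall response, which sits against the primary ORR rule; separately, the PD limit ignores the upper half of the first-scan window

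*Protocol*

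**What the plan says.** **Which assessments count toward ORR.** Section 10.4.1 defines ORR as the proportion of subjects with a BOR of confirmed CR or PR, "as per local review and according to RECIST v1.1 (see Appendix 2 for details"). Appendix 2 (Section 14.2.3.1) asks the protocol to say whether assessments after treatment withdrawal enter BOR. Failing that, "any assessments taken more than 30 days after the last dose of study treatment will not be included in the best overall response derivation". If such assessments are to enter the main endpoint, "then this should be described and justified in the protocol".

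Section 10.4.3 sets no limit relative to the last dose: "For the computation of ORR, all confirmed responses (CR or PR) reported up to the analysis cut-off will be included". It adds: "Subjects with no valid radiological assessment or unconfirmed responses will be considered as non-responders". Sections 7.1.8 and 7.2.1.2 and Table 7-3 require subjects who stop treatment without progression to keep the same scan schedule until progression. None of these sections says whether those scans enter BOR.

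**PD and UNK limits.** The first scan is due 12 weeks after first dose (randomization in the randomized arms), plus or minus 7 days. Section 14.2.3.1 sets SD at more than 11 weeks and PD at 12 weeks or less. UNK takes everyone else, glossed as cases "without SD after more than 11 weeks or early progression within the first 12 weeks". It says that these durations are "based on the first 12-week tumor assessment frequency taking into account time windows for assessment".

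**The concern.** The primary endpoint is derived from a sequence of assessments, and the protocol gives two accounts of where that sequence ends for a subject who stops treatment without progression. A programmer working from Section 10.4.3 uses every scan to cut-off. One working from Section 10.4.1 into Appendix 2 stops 30 days after the last dose. They differ for a subject who responds around the first scan and stops dosing early, for instance under the permanent-discontinuation rules of Section 6.3. The same subjects move in or out of the duration-of-response set, because Section 10.5.1 is restricted to confirmed responders. The trial is open-label and the endpoint is read locally, so the choice should not be left until responses are known.

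The second matter is smaller. The SD limit uses the early edge of the first-scan window, but the PD limit does not use the late edge, although the appendix says the windows were considered.

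**Working it through.** **Inputs.** Dosing every 28 days (Table 6-1). First scan on day 84 ± 7, that is days 77-91, and the next at week 20 ± 7 days, days 133-147 (Table 7-3). Confirmation at least 28 days after response is first seen (Section 7.2.1.2). Appendix 2 default limit of 30 days after last dose. Days are counted from first dose, the scan reference date in arm 1A, with first dose at day 0.

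**Step 1: what the default does to confirmation.** With last dose on day D, the last eligible scan is on day D + 30. A response first seen on day t needs a second scan on day t + 28 or later, so it can be confirmed only if t + 28 ≤ D + 30, that is t ≤ D + 2.

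| Last dose | Last eligible day | Latest confirmable first response | First PR on day 84 | Scheduled week-20 scan |
|---|---|---|---|---|
| Week 4 (day 28) | 58 | day 30 | scan itself excluded | excluded |
| Week 8 (day 56) | 86 | day 58 | counted, but confirmation (day 112 at earliest) excluded | excluded |
| Week 12 (day 84) | 114 | day 86 | confirmable only on days 112-114 | excluded |
| Week 16 (day 112) | 142 | day 114 | confirmable on days 112-142 | eligible on days 133-142 |

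In the week-8 row no first-scan date helps: the earliest in the window is day 77, and 77 + 28 = 105, which exceeds 86. Under Section 10.4.3 the same subject is a responder if a later scan confirms the response.

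**Step 2: the plan's own figures.** Enumerating the arm 1A rule exactly (at least 5/20, then at least 9/40, then at least 23/100) at a true ORR of 30% gives 76.2%, 73.5% and 72.1%, matching Table 10-12. The exact 95% lower limit is 15.2% for 23/100, as stated, and 14.3% for 22/100.

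**Step 3: sensitivity, by assumption only.** The protocol gives no figure for how many responders the cut would remove. If a fraction f of true responders were lost, the observable ORR is 30% × (1 − f):

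| Assumed f | Observable ORR | Crosses first interim | Positive study |
|---|---|---|---|
| 0 | 30% | 76.2% | 72.1% |
| 5% | 28.5% | 71.5% | 65.3% |
| 10% | 27% | 66.2% | 57.3% |
| 20% | 24% | 54.4% | 38.3% |
| 30% | 21% | 41.4% | 19.3% |

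The cut can only remove responders. At a true ORR of 15%, the null value, the full rule succeeds with probability 1.07%, and losing responders can only reduce that.

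**Step 4: the PD limit.** Twelve weeks is day 84, but the window runs to day 91. A first scan on days 85-91 showing PD, with no earlier qualifying scan, is not CR, PR or SD and is later than 12 weeks, so BOR is UNK. That is 7 of the 15 permitted days. If 50 of 100 subjects progressed at the first scan and scans fell evenly over the window (both assumptions), 50 × 7/15 ≈ 23 would be labelled UNK. ORR counts CR and PR, DCR adds SD, and PFS uses the progression date, so none of these moves.

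**The case against.** The strongest reply is that the 30-day rule is labelled a default in generic appendix text, while Section 10.4.3 is specific to this study and its heading covers discontinuations. That section sets its boundary elsewhere, at subsequent anti-cancer therapy, which would add little if a cut at last dose plus 30 days already applied. The mandated off-treatment scans point the same way. Section 14.2.4.1 also lets study-specific issues be settled in the protocol or the analysis-plan documentation, which is not at hand.

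Most of this stands: Section 10.4.3 is probably meant to govern. It does not close the gap. Section 10.4.3 counts confirmed responses, and whether a response is confirmed is itself derived under Appendix 2, so its sentence can be read with the cut still in force. It does not mention off-treatment scans and gives no justification, and Appendix 2 asks for both in the protocol.

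On size, the reply is also fair. An end-of-treatment or unscheduled scan could show response before week 12, though with last dose at week 8 it would have to do so by day 58. In arms 2-4 one drug may continue after the other stops, and capmatinib and ribociclib are daily for all or most of each cycle, so the last dose can fall later than the infusion dates suggest. Among the first 35 subjects of arm 1, Section 2.4.1.1 names progression as the main reason for stopping (57.1%) and mentions one adverse event leading to discontinuation, in a subject who died.

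For the PD limit, suspected progression must be imaged promptly (Section 7.2.1.2) and a PD assessment takes its earliest measurement date (Section 14.2.3.2.7). Both would reduce the number labelled UNK.

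**Conclusion.** The point holds in a limited form. **First part, should-fix:** the primary endpoint depends on a default that the protocol neither adopts nor disapplies. If it were applied, the early-stopping subjects in Step 1 would change from responder to non-responder. **Second part, minor:** the PD limit contradicts its stated basis and misplaces some first-scan progressors in the BOR table.

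A reader might infer more than the protocol supports:

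- That it fixes two different primary endpoints, or that responders will be lost. It does not establish this; Section 10.4.3 can reasonably be read as overriding the default.
- That the power figures in Step 3 are estimates. They show sensitivity to an assumed loss.
- That the result is fragile because one responder separates 22/100 from 23/100. That is true of any binomial cut-off and says nothing about likelihood.
- That subjects stopping for immune toxicity are those with durable responses. The protocol does not say so, and the point does not need it.
- That the PD limit touches efficacy conclusions. It leaves ORR, DCR, PFS and every decision rule unchanged.

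**What to change.** In Sections 10.4.3 and 14.2.3.1, state that all assessments before progression and before the start of subsequent anti-cancer therapy count toward BOR, irrespective of time since last dose, and that the Appendix 2 30-day default does not apply. Add the one-line justification that Appendix 2 asks for; for example, that scans continue on the same schedule off treatment until progression. This wording also settles the case of a response first seen before new therapy and scanned again after it: the later scan does not confirm it. If the sponsor does intend the 30-day limit, Section 10.4.3 should say so instead.

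In Section 14.2.3.1, change the PD limit to 13 weeks or less, align the UNK wording, and define the day count so that the last permitted day of the window falls inside.

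The cost is a few sentences and a programming change. No new data are needed, because the scans are already required. The text should be settled before arm 1A responses are analysed.
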